The exemestane and letrozole pharmacogenomics (ELPh) study, conducted by the Consortium on Breast Pharmacogenomics (COBRA), has provided important data not only regarding the prevalence of the symptoms and drug discontinuation but also for PRO by using the Health Assessment Questionnaire (HAQ), a commonly used rheumatology instrument. [name] and [name] of ECOG are co-founders of the COBRA group. In this prospective comparison of exemestane and letrozole, patients were randomly assigned to either letrozole or exemestane and were evaluated at predefined intervals by study team members and referred to a rheumatologist based upon change in HAQ scores and pain ratings on a visual analog scale (VAS). The study showed that the predefined symptomatic criteria based on the HAQ and VAS successfully provided a means of case definition of an otherwise difficult-to-characterize syndrome (4,5). Improvement or worsening of HAQ score was defined as a decrease or increase, respectively, of more than 0.22 based on data provided from the rheumatology literature⁽¹²⁾. However, the sensitivity, specificity, and generalizability of the ELPh clinical criteria for defining AIMSS clearly need to be confirmed in a larger cohort of a diverse patient population and in other clinical settings. Data from the ELPh study for the first 100 patients showed that median time to onset of symptoms was 1.6 months (range 0.4-10 months), and median time to study discontinuation (for those who stopped taking AI) was 6.1 months (range 2.2-13 months) (4).

Anastrozole was not studied in the ELPh trial, representing a gap in knowledge both as it is a widely prescribed AI, and because anastrozole associated musculoskeletal symptoms have not been phenotypically characterized with the HAQ. Furthermore, as the patients studied by the ELPh and NCIC Clinical Trials Group MA.27 (described below) populations are predominantly Caucasian, further studies in minority populations are urgently needed.

Genetic Predictors of AIMSS: Pharmacogenomic predictors may help identify women at risk for AIMSS since genetic variants that are associated with AI pharmacokinetics, with the effects of estrogen deprivation on bone and other phenotypes have already been described. We briefly review recent important findings that emphasize the importance of this concept as well as its feasibility.

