2.1 Primary Objectives

To validate previously identified associations between 10 specific single nucleotide polymorphisms (SNPs) and discontinuation of treatment with Als due to the development of musculoskeletal symptoms (MSS) among women with breast cancer.

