5.1.1 Treatment

Anastrozole 1 mg, oral, daily for 12 months. Treatment should start within three working days after registration. The patient will be given a pill diary and instructed to complete it and bring it with them to their next MD visit.

5.1.2 Patients should be instructed that when they develop joint pain or stiffness that they should call their MD. Patients should be encouraged to stay on the medication until seen in an office visit.

MD or provider should see the patient within 2 weeks of the patient's call to assess for the likelihood of rheumatologic disease (joints are not red, hot, swollen, or deformed), and determines clinically if the patient has AIMSS, and records his/her impression. The patient completes the questionnaires.

Patient discusses with MD whether to continue or discontinue the drug or start a treatment for AIMSS. A holiday (defined as a drug-free interval of 6 weeks or less) is also an option, as is switching to a different AI, tamoxifen, or participating in a treatment study. The MD will record the recommendation.

- 5.1.3 If and when the patient decides to discontinue anastrozole, the patient will be asked to complete questionnaires. If this was part of a holiday plan, the drug will be considered discontinued if the patient refuses to restart the medication (off the medication for more than 6 weeks).
 - 5.1.3.1 When a patient discontinues the medication, she will be asked for the reasons, and asked to rank them. If pain or other symptoms such as stiffness are the first or second reason, then it will be considered a discontinuation because of AIMSS.
 - 5.1.3.2 The MD will check in with the patient 4-6 weeks later to see if symptoms have resolved, and if anastrozole is discontinued. The patient will complete questionnaires again.

Rev. 11/13

5.1.4 If the patient is to continue anastrozole beyond the 12 months on study, a final questionnaire will be completed at the 12 month time point.

NOTE: All notations of MD above refer to medical protocol (ie, MD, NP or PA); an oncology nurse may also make assessments if felt to be qualified by the Principal Investigator.

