8.1.11 References

AstraZeneca. Arimidex (anastrozole) tablets prescribing information. Wilmington, DE; 2008 Dec.

9. Statistical Considerations

The primary endpoint is defined as discontinuation of treatment following development of AIMSS. A patient will be considered to have developed AIMSS if there is a 20% or greater decline in scores on the HAQ instrument from baseline within one year. At the time of treatment discontinuation, patients and providers will be asked to rank the reasons for treatment discontinuation. If either the patient or the provider lists pain as the first or second-ranked reason and discontinuation is within 3 months of symptom escalation, this will be considered an event. Patients who are lost to follow-up or whose reason for discontinuation is unknown will be considered to be event-free. From previous studies, it is estimated that 40% of patients will develop symptoms, and 25% of patients will discontinue treatment with Als within 1 year due to development of musculoskeletal symptoms.

The enrollment plan is designed to assure adequate enrollment of minority (Asian and African-American) patients. After 600 patients are enrolled from other racial groups, closure of the study to those subgroups will be terminated and accrual will continue among only Asian and African-American patients. When 200 patients are enrolled from the first remaining racial subgroup, closure of accrual to that subgroup will terminate and all remaining patients will be enrolled from the final remaining subgroup. ECOG Minority CCOPs will be strongly encouraged to participate in order to meet targets for minority accrual. While not a separate accrual cohort, ethnicity (Hispanic/non-Hispanic) will also be considered in the analysis plan.

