9.1 Statistical considerations for primary objective of SNP validation

Patients will be classified into two groups based on whether or not they discontinued treatment due to MSS. Hardy-Weinberg equilibrium will be evaluated within each racial subset. SNP genotypes will be coded as additive effects on the log odds ratio by coding as 0, 1 or 2 for the count of the minor allele. Logistic regression will be used to test the association between having a minor allele and the log odds of discontinuation of treatment, adjusting for covariates. We plan to enroll 1000 patients and follow them for development of symptoms. Minor allele frequencies reported by Ingle et al. were assumed for the 4 SNPs associated with the TCL1A gene, and preliminary results from the ELPH study were used to estimate minor allele frequencies associated with the ESR gene. A Bonferroni adjustment will be used to account for the simultaneous testing of 10 SNPs; a one-sided p-value of 0.0025 will be considered statistically significant. For purposes of illustrating statistical power, we assume that Hardy-

Weinberg equilibrium exists in the allele distribution and that the minor allele is associated with *higher* proportions of discontinuation of treatment due to development of symptoms. Table 1 shows the genes, SNPs, and representative minor allele frequencies observed in previous studies. Table 2 shows odds ratios for the effect of each minor allele that will be detectable with 80% power for overall discontinuation rates of 20% or 30% and a range of plausible minor allele frequencies, given a sample size of 1000 patients and using a one-sided Cochran-Armitage trend test. The table also shows detectable odds ratios for the subsets of Caucasian (n=600) and African-American and Asian patients (n=200 patients each).

Table 1. SNPs to be validated

SNP	Gene	Rank (Ingle)	Rank (ELPH)	Minor Allele Frequency (MAF)
rs7158782	TCL1A	1		0.189 among cases, 0.109 among controls (0.2 ELPH)
rs7159713	TCL1A	2		0.189 (0.19 ELPH)
rs2369049	TCL1A	3	4	0.176 (.18 ELPH)
rs11849538	TCL1A	4	9	0.15 (ELPH)
rs2296972	HTR2A		1	0.37 (ELPH)
rs2347868	ESR1		2	0.23
rs9340835	ESR1		3	0.35
rs2234693	ESR1			0.45 (Riancho)
rs1062033	CYP19A1			0.44 (Riancho)
rs4646	CYP19A1		5	0.28

Table 2. Odds Ratios for Effect of Each Minor Allele Detectable with 80% Power (Additive Model)

Proportion Discontinuing	MAF	N=1000	N=600	N=200
20%	10%	1.88	2.23	3.89
30%	10%	1.78	2.10	3.65
20%	20%	1.63	1.87	2.94
30%	20%	1.55	1.76	2.70

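### Section 9's primary-event rule counts only pain, words the HAQ criterion in the wrong direction and starts its window at an undefined point, so it does not match the objective or Section 5.1.3.1

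*Combined protocol and SAP*

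**What the plan says.** **Objective and grouping.** Section 2.1 concerns stopping an aromatase inhibitor "due to the development of musculoskeletal symptoms (MSS) among women with breast cancer". Section 9.1 repeats this for the analysis: "Patients will be classified into two groups based on whether or not they discontinued treatment due to MSS".

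**Event rule in Section 9.** The primary endpoint is stopping treatment after AIMSS has developed. AIMSS is then defined: "A patient will be considered to have developed AIMSS if there is a 20% or greater decline in scores on the HAQ instrument", measured from baseline within one year. At the stop, "patients and providers will be asked to rank the reasons for treatment discontinuation". The event rule follows: "If either the patient or the provider lists pain as the first or second-ranked reason and discontinuation is within 3 months of symptom escalation". The planning rate of 25% at one year is stated for stops due to musculoskeletal symptoms.

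**Rule in the treatment plan.** Section 5.1.3.1 asks the patient to rank her reasons: "If pain or other symptoms such as stiffness are the first or second reason, then it will be considered a discontinuation because of AIMSS". Section 5.1.2 treats both symptoms as the presenting complaint: "Patients should be instructed that when they develop joint pain or stiffness that they should call their MD". It leaves the AIMSS diagnosis to clinical judgement.

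**HAQ direction.** Section 1.1.1 says of the earlier letrozole and exemestane study: "Improvement or worsening of HAQ score was defined as a decrease or increase, respectively, of more than 0.22". Section 6.2.1 says this study adopts that group's symptom assessment scheme.

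**The concern.** One yes/no variable forms the two groups in all ten SNP tests. A rule that sorts women differently from the objective changes what is being validated. A woman who stops for stiffness, with pain ranked first or second by neither her nor her provider, is an AIMSS discontinuation under Section 5.1.3.1 and a control under Section 9. If such stops share the SNP effect, events are lost and the odds ratio moves toward 1.

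Two further parts of the rule cannot be applied as written. The HAQ change runs the wrong way, and the window has no defined start, so two analysts could classify the same woman differently. Choosing among readings after genotypes are known would weaken a study whose purpose is validation.

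**Working it through.** **1. The two rules side by side**

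| Element | Section 5.1.3.1 | Section 9 |
|---|---|---|
| Reason | Pain, stiffness or similar symptoms | Pain only |
| Who ranks | Patient | Patient or provider |
| HAQ criterion | None | 20% decline; unclear whether needed as well as the ranked reason |
| Time window | None | 3 months from symptom escalation |

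Section 9 is narrower on reason and window and wider on who ranks. The net change in the number of events cannot be derived from the documents.

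**2. HAQ criterion.** Under Section 1.1.1 a lower score is better, so a decline is improvement. Reversing the sign is not enough, because a relative change of 20% and an absolute change of 0.22 agree only where 0.20 × baseline = 0.22, that is, at a baseline of 1.10. At a baseline of 0.50, 20% is 0.10. At a baseline of 0 a percentage change is undefined. Entry requires pain of 3 or less out of 10 (3.1.11), so low baselines are plausible.

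**3. Window.** Symptom escalation appears only in Section 9. The schedules in 5.3.2 and 7.1 name baseline, months 3, 6, 9 and 12, symptom onset or AIMSS diagnosis, discontinuation due to AIMSS, and one month after that. None is called escalation.

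**4. Reproducing Table 2.** Inputs from 9.1: N = 1000, one-sided 0.0025 (z = 2.807), additive trend test, Hardy-Weinberg proportions. For minor allele frequency m, the genotype shares g are (1−m)², 2m(1−m) and m² for x = 0, 1, 2. The model is logit p(x) = a + x·ln(OR), with a solved to give the stated overall rate. Let q(x) be the probability of a counted event, q̄ its mean and x̄ = 2m. Then:

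- Δ = Σ g(x−x̄)q
- V0 = q̄(1−q̄)·2m(1−m)
- V1 = Σ g(x−x̄)²[q(1−q̄)² + (1−q)q̄²] − Δ²
- Power = Φ[(√N·Δ − z√V0)/√V1]

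At m = 20%, Table 2's OR of 1.63 (rate 20%) gives 80.6% and its 1.55 (rate 30%) gives 81.0%. All eight N = 1000 entries give 80.4% to 81.6%. Table 2 is sound and is not in dispute.

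**5. Illustration: some true events not counted.** Take rate 25% (250 events), m = 20%, OR 1.57. Then g = 0.64, 0.32, 0.04 and p = 0.215, 0.301, 0.403. Assume a share c of true events is counted, unrelated to genotype, so q = c·p.

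| c | Events counted | Δ | V0 | V1 | Power |
|---|---|---|---|---|---|
| 1.0 | 250 | 0.02849 | 0.0600 | 0.0682 | 79.3% |
| 0.9 | 225 | 0.02564 | 0.0558 | 0.0640 | 72.0% |
| 0.8 | 200 | 0.02279 | 0.0512 | 0.0593 | 63.7% |

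For c = 1: (31.623 × 0.02849 − 2.807 × 0.2449)/0.2611 = 0.817, and Φ(0.817) = 0.793. The apparent OR falls from 1.57 to 1.54 and 1.52. The true OR detectable with 80% power rises from about 1.57 to 1.63 and 1.69.

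**6. The opposite assumption.** Suppose 10% or 20% of the 250 stops are stiffness-led and unrelated to the SNPs. The pain-only rule then has 225 or 200 events at OR 1.57 and power of 76% or 72%. Adding the 25 or 50 unrelated stops from the remaining women, q = p + f(1−p) with f = 25/775 or 50/800, lowers power to 69% or 57%. If those stops are instead equally likely in every genotype, it falls to about 73% or 64%.

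**The case against.** The strongest reply is that Section 9 sets out the primary endpoint and so governs, while 5.1.3.1 is a treatment-plan label that also triggers extra questionnaires. A pain-only event could be a deliberately specific phenotype, since Section 1.1.1 warns about heterogeneous groups. The point on precedence stands: a reader might infer that the plan leaves it wholly open which rule applies, and that goes too far. But the documents nowhere say that pain-only is deliberate, and 2.1 and 9.1 still speak of musculoskeletal symptoms.

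A reader might also infer that improvement will actually be coded as AIMSS. That is unlikely. Sections 1.1.1 and 6.2.1 together make the intended direction plain, and the authors may have meant a decline in function. It is probably a wording slip, but it remains a wrong stated rule.

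A reader might infer that provider rankings are not collected, because footnote 7 in 7.1 mentions only impressions and recommendations. The form's items are not reproduced, so the documents do not show this.

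**Conclusion.** The mismatch holds on the text alone. Followed literally, Section 9 scores stiffness-led musculoskeletal stops as controls, asks for a HAQ change that Section 1.1.1 calls improvement, and applies a window with no defined start. Because this rule makes the primary outcome, it must be corrected before patients are classified.

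Its size is not established. It is tempting to conclude that the study loses 7 to 16 points of power (79% to 72% or 64%). The documents do not support that: the 10% and 20% shares are assumed, the loss is taken as unrelated to genotype, the provider's ranking works the other way, and under the opposite assumption the wider rule costs power. No separate effect can be put on the HAQ wording or the window. The case for change is therefore agreement with the stated objective, not power.

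**What to change.** By a dated amendment, finalised before genotype data are linked to outcomes or by people blind to genotype (Section 10.5 has laboratory data transferred quarterly), give one event definition in Section 9 and have 5.1.3.1 and 9.1 refer to it.

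- **Reason.** Count pain, stiffness or other musculoskeletal symptoms ranked first or second. Keep the pain-only rule as a sensitivity analysis. Confirm that the provider's ranking is captured.
- **HAQ.** State the criterion as a worsening (increase) in a form defined at baseline 0, for example the absolute increase of more than 0.22 cited in Section 1.1.1. Say whether it is required in addition to the ranked reason.
- **Window.** Start it at the earliest dated record of symptoms: the symptom-onset visit or the first HAQ that meets the worsening criterion. Footnote 17 in 7.1 lets a discontinuation visit replace a scheduled one within a month. Where that happens, or no earlier record exists, allow the discontinuation assessment so that these women are not dropped. Report a no-window sensitivity analysis.

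The cost is an amendment to the primary endpoint definition. The HAQ, patient rankings and symptom-onset visit are already planned. The downside is that some less specific stops will count as events. In the illustration above, scoring 2% or 5% of the 750 true non-events (15 or about 38 women) as events lowers power from about 79% to about 75% or 70%. Recovering 25 or 50 missed events still raises power unless the wider rule adds more than about 28 or 59 false ones. This concerns analysis coding only, not when treatment is stopped.

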Collection of patient rated outcomes is a critical component of these kinds of studies, and incomplete data collection during follow-up represents a major challenge both logistically and to the validity of these studies. The NIH has developed a Web-based system for recording patient reported outcomes during clinical trials, the Patient Reported Outcomes Management Information System (PROMIS) that will enable the efficient collection of patient reported outcomes and decrease the logistical burdens on office practices for patients on clinical trials. The PROMIS Assessment Center is the web-based platform for dissemination of NIH PROMIS measures. The assessment center can be used to administer patient rated outcome instruments, monitor accrual, manage data, send reminders to patients, be used to deliver custom researcher developed content, and has numerous features that support both simple and complicated accrual designs (branching, multiple arms, multiple time points, etc.). (25) [name], an ECOG member, has been a key participant in the development of the PROMIS system and is Director of the PROMIS Statistical Center. Studies undertaken by the PROMIS staff have shown there is excellent satisfaction with the PROMIS Assessment Center (26) for patients with visual and other impairments. There is no charge for using the PROMIS system. Data is kept secure behind firewalls. Data that is entered will be the property of ECOG and can be downloaded directly to the ECOG system. With the current popularity of smart phones in the breast cancer patient population, we think the time is ripe to test its' use in a cooperative group trial setting.

The symptom instruments used will build upon the work in the NIH Patient Reported Outcomes project to develop better symptom instruments, through use of the PROMIS Physical Function 20 Form and the PROMIS Assessment Center. This will support the development of better symptom and quality of life measurements and begin to integrate the PROMIS project within the Cancer Cooperative Groups. Experience in using the instruments and the PROMIS Assessment Center will lead to new ways for cooperative groups to collect patient rated outcome data and reduce attrition.

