2.2 Secondary Objectives

- 2.2.1 To determine whether other SNPs in CYP, UGT, Vitamin D, serotonin and other receptors are associated with discontinuation of treatment due to the development of severe AIMSS.
- 2.2.2 To determine whether other SNPs in CYP, UGT, Vitamin D, serotonin and other receptors are associated with the development of other potential complications of AI therapy.
- 2.2.3 To develop a gene signature that can identify patients at risk for developing severe anastrozole-related AIMSS and other potential complications of AI therapy.
- 2.2.4 To determine the epidemiology and predictors of severe AIMSS and of AI discontinuation.
- 2.2.5 To describe patient reported outcomes for minority patients with breast cancer treated with aromatase Inhibitors (Als).
- 2.2.6 To assess the utility of the PROMIS system to collect patient reported outcomes in a cooperative group study, and validate the PROMIS Physical Function 20a form in patients with AIMSS.
- 2.2.7 To develop a model that incorporates patient ratings of treatment burden, fear of recurrence and adherence behaviors to describe patient decisions to continue or discontinue anastrozole.
- 2.2.8 To collect serum samples for future testing for biomarkers of AIMSS.

Rev. 11/13

Rev. 11/13

3. Selection of Patients

ECOG Patient No.

Each of the criteria in the checklist that follows must be met in order for a patient to be considered eligible for this study. Use the checklist to confirm a patient's eligibility. For each patient, this checklist must be photocopied, completed and maintained in the patient's chart.

In calculating days of tests and measurements, the day a test or measurement is done is considered Day 0. Therefore, if a test is done on a Monday, the Monday four weeks later would be considered Day 28.

Patient's Initials (L, F, M)							
Physician Signature and Date							
NOTE:	All questions regarding eligibility should be directed to the study chair or study chair liaison.						
NOTE:	Institutions may use the eligibility checklist as source documentation if it has been reviewed, signed, and dated prior to registration/randomization by the treating physician.						
3.1 Eli	gibility Criteria						
3.1	I.1 Age ≥ 18 years.						
3.1	Patients must be female and post-menopausal. Post-menopausal will be defined as women meeting any of the following criteria:						
	 ≥ 60 years of age; or 						

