20%	30%	1.55	1.76	2.66
30%	30%	1.47	1.65	2.42
20%	40%	1.52	1.72	2.59
30%	40%	1.44	1.61	2.33

9.2 Secondary Endpoint Analyses

The association of other SNPs in the ESR, TCL1A, and CYP19A1 genes with discontinuation of treatment due to MSS will be explored using a candidate gene approach. In this exploratory analysis, the prevalence of treatment

discontinuation will be compared between patients who do and do not have the variant genotype, modeling the effects as additive, dominant, and recessive. Correlations among SNPs will be estimated, and linkage disequilibrium among pairs of SNPs will be characterized. Logistic regression models, with treatment discontinuation as the outcome variable, will be used to explore the association with SNPs, adjusting for important clinical factors. No adjustment for multiple comparisons is planned, but only the top ranking SNPs that were not part of the primary validation study will be further explored.

Other endpoints, including the proportions of patients with treatment discontinuation for any reason, the proportion of patients with symptoms determined not to be from other known etiologies, and the proportion of patients whose symptoms improve when the AI is discontinued, will be similarly explored. Time to discontinuation of treatment and time to development of symptoms will be explored using proportional hazards models adjusting for significant genotypic and clinical predictors. Kaplan-Meier plots will be used to graphically portray the associations. Hispanics are the fastest growing demographic group in the US population, and there are 17,100 new breast cancer cases and 2400 breast cancer deaths expected in this demographic group in 2012³⁷. The Hispanic demographic group may have unique attitudes, beliefs and behaviors related to medication adherence with AI.³⁸⁻⁴⁰ Exploratory analyses to determine whether effects are different in patients with Hispanic ethnicity will also be performed.

Previous studies have suggested that patients who experience specific adverse events associated with endocrine therapy may have improved recurrence-free (RFS) and overall survival (OS) compared to those who do not develop these symptoms (42,43). RFS ad OS will be described for the entire study population and for racial and ethnic subsets. Differences in RFS and OS between patients who do or do not develop AIMSS will be explored.

9.3 Statistical Considerations For Patient-Reported Outcomes

Rev. 11/13

Rev. 11/13

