We propose to include all 1000 patients in assessment of patient-reported outcomes. Linear mixed effects models will be used to evaluate changes in symptoms over time on these instruments. For purposes of estimating available statistical power, we consider a hypothetical analysis comparing changes in endocrine symptoms from baseline to 3 months between Caucasian and African-American patients. Total score on the FACT-ES (FACT-B plus ES subscale) will be calculated. Psychometric properties of FACT-ES were reported by Fallowfield et al. (29). In that report, mean scores of 61.61 at baseline (standard deviation 6.65) and 57.03 at 12 weeks (standard deviation 9.03) were reported among 32 women (a decline of 4.52 points). Table 3 shows statistical power and differences in change from baseline that will be detectable assuming a two-sided t-test with 5% Type I error, 85% power, baseline standard deviation of 6.65, intrapatient correlations of 0.4 or 0.6, and QOL completion rates of 90% and 75% across the two time points. There will be good power to detect reasonable differences between groups in changes from baseline.

Table 3. Detectable Differences for an Example Patient-Reported Outcomes Analysis (85% Power)

Intra-Patient Correlation	Standard Deviation of Change	Completion Rate	N Caucasian Patients	N African- American Patients	Detectable Difference
0.4	7.285	90%	540	180	1.88
0.6	5.948	90%	540	180	1.54
0.4	7.285	75%	450	150	2.06
0.6	5.948	75%	450	150	1.68

Rev. 11/13

Similar analyses will be done for the FACT-B subscale and for the Trial Outcome Index, consisting of the FACT-B subscale along with the FACT-G Physical Wellbeing and Functional Well-Being subscales.

In E1Z03, the quality of life companion study to MA27, patients who reported being bothered by side effects of treatment were more likely to discontinue treatment. The impact of patient-reported outcomes, both side effects in general and joint pain in particular, on treatment discontinuation will be examined along with the genotype information to assess the relative significance of both.

Patients will be given a choice regarding their preference for submitting QOL instruments in paper form or electronically. If 90% or more of patients choose the electronic system and if the completion rate among those patients is greater than 90%, then the web-based system would be considered for future trials.

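### Scoring women who are lost, or who stop for an unknown reason, as event-free can only lower (or leave unchanged) the recorded AIMSS discontinuation rate, and no planned analysis re-scores them

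*Combined protocol and SAP*

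**What the plan says.** The opening of Section 9 defines the primary endpoint as stopping treatment after AIMSS develops, and fixes the handling of unresolved women: "Patients who are lost to follow-up or whose reason for discontinuation is unknown will be considered to be event-free". Section 9.1 then states: "Patients will be classified into two groups based on whether or not they discontinued treatment due to MSS". It fits a covariate-adjusted logistic regression and makes no allowance for loss in the power table. Section 9 expects that "25% of patients will discontinue treatment with Als within 1 year due to development of musculoskeletal symptoms".

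Section 1.1.3 recognises the general risk: "incomplete data collection during follow-up represents a major challenge both logistically and to the validity of these studies". Several sections try to limit it:
- Section 5.8 follows early stoppers to month 12.
- Section 5.3.2 asks sites to attempt questionnaires by mail or remote entry when a visit is missed.
- Sections 5.1.3.1 and 9 ask for ranked reasons at stopping, from the patient and from both patient and provider respectively.
- Section 7.1 schedules a Physician Questionnaire when anastrozole is stopped for AIMSS.

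Section 9.2 lists related exploratory analyses: "the proportions of patients with treatment discontinuation for any reason", and "Time to discontinuation of treatment and time to development of symptoms will be explored using proportional hazards models", with Kaplan-Meier plots.

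**The concern.** The rule fills in a missing outcome with one fixed value, the same for every woman concerned. With E known events among N women, it records E/N. If x of the unresolved women truly stopped for AIMSS, the rate would be (E + x)/N, and x cannot be negative. The recorded rate is therefore the lowest the data allow.

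The two groups differ. A woman lost part-way may have had no event at all. A woman who stopped for an unknown reason is known to have stopped, so scoring her event-free hides more events per woman.

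What is at stake is mainly the descriptive rate of AIMSS discontinuation. The nearest objective is 2.2.4 ("To determine the epidemiology and predictors of severe AIMSS and of AI discontinuation"). The Section 9.2 analyses give partial cover only. They are exploratory, are not stated to be specific to AIMSS, and state no censoring rule. Any-reason discontinuation does count unknown-reason stops as events, but mixes them with stops known to be for other causes.

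**Working it through.** **Inputs from the plan.** N = 1000; one-sided level 0.0025 (0.025/10 SNPs); additive coding 0, 1, 2; Cochran-Armitage trend test; Hardy-Weinberg proportions (Section 9.1); event rate 25% (Section 9).

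**Assumptions.** Minor allele frequency 20%. Share lost, L, 10% or 20%. Share of stops without a reason, u, 10% or 20%. Women stopping for other reasons, 10%. The plan gives none of the last three. The completion figures in Section 9.3 ("QOL completion rates of 90% and 75% across the two time points") concern questionnaires and are not loss rates.

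**1. Reproduce the plan's power table.** With genotype weights w, risks p, overall rate P and mean allele count m:
- U = Σ w p (x − m)
- V0 = P(1 − P) Σ w (x − m)²
- V1 = Σ w p(1 − p)(x − m)²
- power = Φ[(√N·U − 2.807·√V0)/√V1]

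At the Table 2 odds ratios this gives about 80% to 82%, so the table reproduces.

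**2. Base case.** A per-allele odds ratio of 1.572 at a 25% rate gives genotype risks of 21.5%, 30.1% and 40.4%. Then √N·U = 0.904, √V0 = 0.245 and √V1 = 0.257. Power = Φ[(0.904 − 0.688)/0.257] = Φ(0.84) = 80%.

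**3. Recorded rate.**
- Women lost, with loss and events both even over 12 months and unrelated: half of the lost women's events fall after loss. The rate is 0.25 × (1 − L/2), which is 0.25 × 0.95 = 23.75% or 0.25 × 0.90 = 22.5%. The shortfall is 1.25 or 2.5 points. One standard error of the rate is √(0.25 × 0.75/1000) = 1.37 points. Censoring the lost women returns 25.0%.
- Unknown reason, at random among stops: 0.25 × (1 − u) = 22.5% or 20.0%. All stops are 25% + 10% = 35%, so 35 or 70 women are concerned. Counting them as AIMSS gives 22.5% + 3.5% = 26.0% or 20.0% + 7.0% = 27.0%. The two scorings bracket 25%.
- Lost women at twice the risk of the others, overall rate still 25%: their risk is 2 × 0.25/(1 + L) = 45.5% or 41.7%. The recorded rate is 0.25 − L × risk/2 = 22.7% or 20.8%. Censoring gives 23.8% or 22.9%, a partial correction.

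**4. SNP test, loss or missing reason unrelated to genotype.** Multiply each genotype risk by the share of events kept, then refit and recompute power.

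| Case | Share kept | Odds ratio | Power |
|---|---|---|---|
| None unresolved | 1.00 | 1.57 | 80% |
| 10% lost | 0.95 | 1.56 | 76% |
| 20% lost | 0.90 | 1.55 | 73% |
| 10% of stops unknown | 0.90 | 1.55 | 73% |
| 20% of stops unknown | 0.80 | 1.52 | 64% |

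Excluding the lost women instead (N = 900 or 800, odds ratio 1.57) gives about 75% or 68%, below the rule.

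**5. All-or-none scoring of women lost.** Scoring all of them as AIMSS gives 0.25(1 − L) + L = 32.5% or 40.0%. The incidence bounds are therefore 23.75% to 32.5%, or 22.5% to 40.0%. The odds ratio under all-AIMSS scoring is 1.43 or 1.34. Both extremes pull it toward 1, so they do not bound it.

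**The case against.** The strongest defence is that the rule is explicit, prespecified and counts only confirmed cases, which suits a study whose main task is to validate SNPs against a clear phenotype. For women lost this largely stands: the odds ratio barely moves, and power is better than under exclusion. Every recorded rate in step 3 also stays within the 20% to 30% range used for Table 2, although that range does not allow for the slight attenuation of the odds ratio.

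A second defence is that reasons are sought from both patient and provider, so unknown-reason stops should be few. That is fair. The fall in power to about 73% or 64% in that group arises only if 10% or 20% of stops lack a reason, and nothing in the documents says they will.

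A third is that objective 2.2.4 names severe AIMSS and AI discontinuation, not discontinuation caused by AIMSS. That also stands. The link to this objective, and the expectation that the rate will be reported as a crude proportion, are inferences.

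A reader might infer that the rule invalidates the primary SNP test, or that the endpoint as a whole is biased low. The documents support neither. Loss related to genotype could move the odds ratio either way, but they give no reason to expect it. Other parts of the definition, such as accepting pain ranked second by either rater, could raise the rate.

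None of this supplies an analysis that re-scores the unresolved women for AIMSS discontinuation.

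**Conclusion.** The point holds as a limited one. The direction is certain for this rule taken alone; the size is not, because the plan states no rate of loss or unknown reason. Under the assumptions above, the recorded rate falls short of a true 25% by 1.25 to 2.5 points for women lost at random, and by 2.5 to 5 points for unknown-reason stops. If lost women are at twice the risk, the shortfall is 2.3 or 4.2 points. The primary test remains sound when loss is unrelated to genotype. This is an inexpensive improvement to how the rate is estimated and reported, and not a defect in the validation design.

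**What to change.** Keep the logistic regression, the 0.0025 level and Table 2 as the primary test, and prespecify three additions.

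1. Wherever the AIMSS discontinuation rate is reported, give 12-month cumulative incidence, overall and by cohort. Censor women lost at last contact, and treat stopping for another known reason as a competing event. Present unknown-reason stops as a pair of equal standing: once as a competing event, once as AIMSS. The first alone does not correct for them; with unknown reasons only, it gives the same 22.5% or 20.0% as the rule.
2. For the 10 SNPs, add one sensitivity analysis: the Section 9.2 hazards model made specific to AIMSS discontinuation, with women lost censored and unknown-reason stops counted as AIMSS.
3. Report the numbers lost and the numbers with unknown reason, by cohort and by genotype. If all-or-none scorings are shown, use them as bounds for the incidence only, not for the odds ratio.

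The cost is SAP wording and a little analysis, with no new data. Censoring assumes loss is unrelated to pain, so it removes only part of the bias if lost women are at higher risk. The incidence bounds will be wide if loss is large.
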